3 OBJECTIVES AND ENDPOINTS

4 STUDY PLAN

4.1 Study Design

This is a Phase 2a, Proof-of-Concept (POC), prospective, multicenter, randomized, double-masked, sham-controlled study to assess the safety, tolerability, evidence of activity and durability of a single IVT injection of UBX1325 in subjects with DME. Approximately 62 total patients will be enrolled 1:1 in the UBX1325 or sham study arms, in order to assess the primary objective. All patients will be followed for approximately 48 weeks.

See Section 6.6 for details on double-masking and site requirements. A schematic representation of the study design is presented in Figure 1.

4.2 Design Rationale

4.2.1 Patient Population Selection

Based on the in vitro and in vivo pharmacology and toxicology data (UBX1325 Investigator Brochure), scientific rationale (see Section 2.3), and safety data from the UBX1325-01 First-in-Human study, the Sponsor asserts that UBX1325 can be tested for safety and efficacy in DME patients.

Patients will be those diagnosed as having DME (as defined by the AAO PPP DME Guidelines 2019) with BCVA in the study eye of 73 to 20 ETDRS letters (equivalent to 20/40 to 20/400 on the Snellen chart).

4.2.2 Dose Rationale

The planned dose is 10 µg based on favorable safety data in the Phase 1 SAD study. As of November 9, 2021, in patients with advanced DME and wet AMD in the SAD Phase 1 study, UBX1325 was well tolerated with favorable safety profile supporting further clinical development; no dose-limiting toxicities in any of the dose cohorts, including the high dose of 10 µg. The planned dose is 10 µg based on favorable safety data in the Phase 1 SAD study.

4.3 Recruitment

Approximately 62 patients are planned to enroll in this study.

4.4 Definitions

Patients officially enter the Screening Period following provision of informed consent directly.

A screen failure is a consented patient who has been deemed ineligible on the basis of 1 or more eligibility criteria or who has withdrawn consent prior to randomization. Screen failures may be rescreened. Patients will be permitted to re-screen once, and in consultation with the Sponsor's Medical Monitor.

An enrolled patient is one who has been deemed eligible and has been randomized.

4.5 Inclusion Criteria

To be included in this study, each individual must satisfy all of the following criteria:

- 1. Patients aged \geq 18 years.
- 2. DR (PDR and NPDR) patients with DME (ETDRS-DRSS Score at 65C [or DR severity level of 8] or less severe as determined by a Central Reading Center), who had at least 2 anti-VEGF intravitreal (IVT) injections (one or more of the following agents: aflibercept, bevacizumab or ranibizumab) in the preceding 6 months prior to Day 1, with the last anti-VEGF given between 3 and 6 weeks prior to Day 1.
- 3. Center-involved DME with central subfield thickness (CST) \ge 300 µm on SD-OCT at Screening as determined by a Central Reading Center.
- 4. BCVA in the study eye (most affected) of 73 to 20 ETDRS letters (equivalent to 20/40 to 20/400 on the Snellen chart) at Screening and at Day 1. If both eyes are equal, then it's Investigator discretion.
- 5. $IOP \le 23$ mmHg in the study eye on Day 1.
- 6. Clear ocular media and adequate pupillary dilation to permit CFP and adequate BCVA evaluation.
- 7. Patients who have the capacity to give informed consent and who are willing and able to comply with all study-related procedures and assessments.

4.6 Exclusion Criteria

If an individual meets any of the following criteria, he or she is ineligible for this study:

- 1. Concurrent disease in the study eye or structural damage, other than DME, that could compromise BCVA, prevent BCVA improvement, require medical or surgical intervention during the study period, confound interpretation of the results, or interfere with assessment of toxicity or CFP in the study eye. This includes, but is not limited to, the following:
 - Macular edema of etiologies other than diabetes
 - Clinically significant subretinal fibrosis
 - Subfoveal lipid
 - Cataract requiring surgery during the study period
 - RPE atrophy or tear or rips involving the macula
 - Clinically significant macular hole
 - Clinically significant noninfectious uveitis
 - Vitreomacular traction
 - Clinically significant epiretinal membrane (ERM)

- Aphakia
- Pseudophakia with anterior chamber intraocular lens (A/C IOL)
- 2. $HbA1c \ge 12$ and/or recent signs of uncontrolled diabetes
- 3. Any ocular/intraocular/periocular infection or inflammation in either eye in the past 4 weeksprior to Screening (mild blepharitis is acceptable)
- 4. History of vitreous hemorrhage in the study eye within 2 months prior to Screening
- 5. History of vitrectomy in the study eye
- 6. History of intraocular, periocular, or corneal surgery in the study eye within 3 months prior to Screening, or anticipated need for such surgery during the study
- 7. History of panretinal photocoagulation (within 3 months) or macular laser photocoagulation (within 3 months) in the study eye prior to dosing
- 8. History of corneal transplant in the study eye
- 9. Patients with glaucoma who are poorly controlled in the opinion of the investigator or on more than 3 meds
- 10. Any condition, including laboratory findings and findings in the medical history or in the pre-study assessments, that, in the opinion of the Investigator, constitutes a risk or contraindication for participation in the study or that could interfere with the study objectives, conduct, or evaluation or prevent the patient from fully participating in all aspects of the study
- 11. Presence of severe myopia (-8 diopters or greater) in the study eye
- 12. History of systemic or intraocular steroid use for or in the study eye for 6 months prior to Day 1. The use of intravitreal nonbiodegradable steroid implants (ex. Iluvien®, Yutiq®, Retisert®) is prohibited
- 13. Significant media opacities, including cataract, which might interfere with VA, assessment of toxicity, or fundus imaging
- 14. Intraocular surgery, including cataract surgery, in the study eye ≤ 3 months of screening
- 15. Known allergy to dye injected during FA
- 16. Known allergy to any component (phosphate buffered saline and polysorbate 80) in the Study Drug. Refer to the Investigator Brochure for more details.
- 17. Female patients who are pregnant, lactating, or of childbearing potential who do not agree to use highly effective methods of birth control (e.g., progesterone-only hormonal contraception, double barrier, or intrauterine device) during the study and for 3 months following the last dose of Study Drug. Postmenopausal females (> 45 years old and without menses for more than 1 year) and surgically sterilized females are exempt from these requirements.
- 18. Male patients who do not agree to use a highly effective method of contraception during the study and for 3 months following the last dose of Study Drug, if sexually active with a female partner of childbearing potential.

- 19. Patients who within 3 months of screening received or are concurrently on another investigational drug or vaccine study, including patients who previously received treatmentin a UBX1325 study. COVID vaccinations are permitted prior to or during the course of the study.
- 20. Any uncontrolled medical condition, in the opinion of the Investigator, would preclude participation in this study, including, but not limited to, history of malignancy within the last 5 years (not including stable, superficial basal or squamous cell carcinoma of the skin), history of myocardial infarction within the last 6 months, or concomitant therapy.

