Exclusion Criteria 5: History of IVT, subconjunctival, or periocular steroids in the 3 months prior to screening conflicts with Exclusion Criteria 13: History of systemic and intraocular steroid use for 6 months prior to Day 1. The use of intravitreal nonbiodegradable steroid implants (ex_Iluvian®) Yutia®	Retaining Exclusion Criteria #13 (now documented as #12 in this amendment) as a higher standard reflects the scientific rigor and safety precautions taken in this study population.
Retisert® is prohibited.	
Exclusion Criteria #5 has been removed.	
[Section Number 4.6 Exclusion Criteria]	
Post-dilution solutions for clinical administration will be held no more than 1 hour at room temperature prior to administration to the patient.	The original hold times and conditions were inaccurate. This change was made to align with guidance in the Pharmacy Manual.
[Section Number 6.1.1 UBX1325]	

The following summarizes the principal elements requiring that change be made to the protocol. Other minor modifications for administrative purposes have been made to provide clarity and are captured in the redlined document.

T1				falana	4 - 41	atra des aus	1	1 1.	a tal.1 a 1	1 1
Ine	princi	pai com	ponents c	of change	to the	study are	described	1 m un	le table	below.

Area of Change	Rationale
Screening window was increased from 28 days to 42 days [Section 1.2 Schedule of Events Table 1] and [Section 5 Study Conduct]	Linking the window acceptable for screening period to coincide with the optimal timing post last anti-VEGF injection (see item 3). The number of days permitted for screening is increased to avoid a patient falling outside the screening window due to when they received their last anti-VEGF treatment and having to rescreen.
[Section 4.2.2 Dose Rationale]	Assessment Committee (SAC) in UBX1325-01 study. On 18May2021, the SAC confirmed that $10 \ \mu g$ should be used in all future UBX1325 study enrollments.

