However, corticosteroids have been shown to interfere with many regulatory components of gene expression inhibiting the expression of VEGF and key proinflammatory genes (tumor necrosis factor α and other inflammatory chemokines), while inducing gene functioning as anti-inflammatory factors (pigment epithelium-derived growth factor [PEDF]) (Tsaprouni et al., 2002; Tong et al., 2006; Kim et al., 2019; Zhang et al., 2006). The anti-inflammatory activity of steroids is also related to the inhibition of the phospholipase A 2 pathway, to the lower release of inflammatory cell mediators, and to the reduced leukocyte chemotaxis (Bandello et al. 2017). Additionally, triamcinolone acetonide (TA) seems to reduce the expression of matrix metalloproteinases (MMPs) and down-regulates ICAM-1 on choroidal endothelial cells (Mizuno et al., 2007). IVT and peribulbar injections of TA must be repeated every 2 to 4 months to maintain effect. Several steroid applications have been studied, for example, biodegradable dexamethasone extended release implant (Ozurdex®), fluocinolone acetonide (Iluvien®) and TA implants to prolong the intervals between treatments (Bandello et al., 2017).

Side effects of steroids are a concern, especially considering the availability of anti-VEGF medications that have minimal ocular side effects. The primary risks associated with IVT administration of corticosteroids for DME are cataract progression and development of glaucoma, which is why it is sometimes contraindicated in patients with glaucoma or ocular hypertension. Nonetheless, steroid treatment can be considered first line in special populations such as, patients who have had a recent history of cardiovascular event, pregnant women, patients unable to adhere to monthly treatments, or DME in eyes undergoing cataract surgery (Zur et al., 2019).

Surgical vitrectomy was proposed as a treatment option for DME in the early 1990s. Eyes with DME were observed to have lower prevalence of posterior vitreous detachment than eyes without DME, and it was thought that vitreomacular adhesion might promote DME. This was further supported by the observation that resolution of DME could occur after

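### Exclusion 12 names only systemic and intraocular steroid, so a recent periocular or subconjunctival depot in the study eye is kept out only by judgement

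*Protocol*

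**What the plan says.** Prior steroid is dealt with in one criterion, Exclusion 12 in Protocol section 4.6. Its first sentence is "History of systemic or intraocular steroid use for or in the study eye for 6 months prior to Day 1". Its second is "The use of intravitreal nonbiodegradable steroid implants (ex. Iluvien®, Yutiq®, Retisert®) is prohibited". The routes named are therefore systemic, intraocular and, for implants, intravitreal.

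Two other criteria in 4.6 use the word periocular, and neither concerns steroid. Exclusion 6 covers surgery: "History of intraocular, periocular, or corneal surgery in the study eye within 3 months prior to Screening". Exclusion 3 covers infection or inflammation: "Any ocular/intraocular/periocular infection or inflammation in either eye in the past 4 weeksprior to Screening". Both list intraocular and periocular as separate terms.

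Protocol section 2.2 describes steroid injection as a treatment for DME and says of triamcinolone: "IVT and peribulbar injections of TA must be repeated every 2 to 4 months to maintain effect".

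The amendment summary at the front of the protocol explains how the present text arose. A former exclusion read "History of IVT, subconjunctival, or periocular steroids in the 3 months prior to screening". It was found to conflict with the 6-month rule, the 6-month rule was kept as the higher standard, and "Exclusion Criteria #5 has been removed". This is history only; the point rests on the current criteria.

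**The concern.** A peribulbar or subconjunctival injection is neither systemic nor intraocular. The phrase about use for or in the study eye does not widen the criterion, because the two adjectives still fix the route. Read as written, Exclusion 12 lets through a patient who received peribulbar triamcinolone in the study eye a few weeks before Day 1.

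The protocol otherwise takes care over residual treatment effect at baseline. The last anti-VEGF injection must fall 3 to 6 weeks before Day 1 (Inclusion 2), laser has a 3-month look-back (Exclusion 7), and intraocular steroid has a 6-month look-back. The periocular and subconjunctival routes have none.

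What is at stake is the Day 1 reference value. If a depot is holding CST down on Day 1 and then wears off, the rise in CST has nothing to do with the study treatment. One arm of the rescue criteria is a 75 µm worsening in CST from Day 1 (Protocol 5.1.10), so wear-off can trigger rescue. Rescue is itself a secondary endpoint, and the main BCVA analysis uses only data up to the rescue date (SAP 7.1), so an early rescue also removes that patient's later BCVA values from it.

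**Working it through.** The plan gives no figure on this point to reproduce. The check is a reading of every rule that could close the gap, followed by date arithmetic.

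**Step 1: does any other rule cover these routes before Day 1?**

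| Rule | What it reaches | Closes the gap? |
|---|---|---|
| Exclusion 12 | Systemic or intraocular steroid, 6 months; intravitreal nonbiodegradable implants | No |
| Exclusion 3 | Periocular infection or inflammation | No |
| Exclusion 6 | Periocular surgery | No |
| Exclusion 10 | Any finding, including medical history, that the investigator thinks could interfere with the study | By judgement only; no route or washout named |
| 6.8.1 | Steroid permitted during the study, including locally injected steroid with epidural and joint injection as examples | No; governs concomitant use |
| 6.8.2, DME treatment | DME treatment of the study eye after randomization | No; starts too late |
| 6.8.2, systemic steroid | Oral, intramuscular and intravenous routes | No |
| 6.8.2, general medication rule | Study-eye medication that the investigator or Medical Monitor thinks may affect results | By judgement only; worded for medication being received |

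No listed criterion names periocular or subconjunctival steroid. Two opinion-based rules could be used against it.

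**Step 2: how long could a depot act after Day 1?**

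Inputs: the 2 to 4 month interval for peribulbar triamcinolone (Protocol 2.2). Assumptions: the retreatment interval equals the duration of effect, and a month is 30.4375 days.

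- Lower end: 2 × 30.4375 / 7 = 8.7 weeks.
- Upper end: 4 × 30.4375 / 7 = 17.4 weeks.
- End of effect, in weeks after Day 1 = duration − k, where k is the number of weeks before Day 1 at which the depot was given.

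| k (weeks before Day 1) | 8.7 − k | 17.4 − k |
|---|---|---|
| 0 | 8.7 | 17.4 |
| 4 | 4.7 | 13.4 |
| 8 | 0.7 | 9.4 |
| 12 | −3.3 (gone before Day 1) | 5.4 |

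A depot given 4 weeks before Day 1 would therefore wear off at about Week 5 to Week 13. Rescue is possible from Week 2, and Week 12 is both the first BCVA endpoint and the interim analysis (SAP 3.6), so wear-off can fall inside the period that these use.

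**Step 3: would the design or analysis absorb it?**

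Randomization is stratified only by the last anti-VEGF agent (Protocol 6.2). The MMRM has baseline value, arm, visit and arm-by-visit terms (SAP 7.1). The subgroups are baseline BCVA, CST, DR severity and HbA1c (SAP 7.3). Prior steroid appears in none of these. SAP 7.1 removes patients who violated major eligibility criteria, but a patient with a periocular depot has not violated Exclusion 12 as written, so that rule would not remove them.

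**The case against.** The case for leaving the text alone has real weight.

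- **Judgement is a safeguard.** Exclusion 10 expressly reaches medical history, and the general medication rule in 6.8.2 is not tied to randomization. Many investigators would turn such a patient away. This stands, so the patient is not positively permitted. But neither rule names a route or a washout, so sites may apply them differently.
- **Few patients are likely.** Inclusion 2 requires at least two anti-VEGF injections in the 6 months before Day 1, the last 3 to 6 weeks before. A periocular steroid would have to come on top of that, in an eye still at 300 µm CST or more at Screening. This stands, although nothing in those criteria prevents added periocular steroid.
- **Wear-off is already in the design.** Every patient enters with a waning anti-VEGF effect, so a rare steroid depot only adds to that. This also stands, but the anti-VEGF window is fixed for everyone and the depot's timing is not.
- **The duration is inferred.** Section 2.2 gives a retreatment interval, not a measured duration, and only for intravitreal and peribulbar triamcinolone. The arithmetic is conditional on that assumption.
- **The amendment summary describes superseded text.** Its difference from the current criteria is not an error, and it is not counted as one here.

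A reader might go further and infer that the 2 to 4 months also applies to subconjunctival steroid. The documents give no interval for that route. A reader might also expect steroid-related pressure rise and cataract to distort the safety comparison. Section 2.2 ties those risks to intravitreal steroid, so the documents do not support carrying them over to periocular use.

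**Conclusion.** The gap is real in the current text. For periocular and subconjunctival steroid in the study eye there is no stated look-back, and only opinion-based rules stand in the way. Following the listed criteria exactly can admit a patient whose Day 1 CST is held down by a waning depot.

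The consequence is limited. It is tempting to read this as bias in the treatment comparison, but allocation is randomized, so such patients can fall in either arm. What remains is added noise and possible chance imbalance in CST change, rescue and the rescue-limited BCVA analysis up to Week 12, with no adjustment planned for it. The size cannot be computed, because the documents do not say how many patients had such treatment; the number is probably small. Dividing one patient by the 31 in an arm would not measure it either, since that fraction is the same for any single patient.

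The timing of about Week 5 to 13 rests on the retreatment interval being the duration of effect, on peribulbar triamcinolone, and on a depot given 4 weeks before Day 1. The criterion should be corrected, but it does not undermine the trial.

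**What to change.** Reconcile Exclusion 12 with section 2.2. Name the periocular and subconjunctival routes in the study eye and put them under a stated look-back, for example by extending the one already there. The exact routes and washout are for the sponsor to set.

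For patients already enrolled, flag any such use in the recorded medication history. Protocol 5.1.3 has medications entered in the eCRF, and SAP 6.3 already codes and lists prior and concomitant medications. If any patient is flagged, repeat the BCVA and CST analyses without those patients as a sensitivity analysis. One limit should be stated with the result: 5.1.3 sets an explicit 6-month look-back for anti-VEGF but not for steroid, so earlier periocular use may be incompletely recorded.

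The cost is a one-line amendment, a few more screen failures and one small extra analysis.

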5 STUDY CONDUCT

The expected duration of study participation for patients will be approximately 54 weeks, which includes a 6-week screening period, a single dose at Visit 1, and 48 weeks of follow-up.

The study procedures are outlined below and in the SoE (Table 1).

dy Procedures
Ĺ

5.1.1 Study Screening and Treatment Periods

- 5.1.1.1 Screening Period (Day -42 to Day -1)
- Informed Consent
- Demographics
- Medical and Ophthalmic History
- Medication History/Concomitant Medications
- Physical Examination
- Vital Signs and Weight
- Height
- Laboratory Tests: Hematology and Chemistry
- Pregnancy Test (serum)
- 12-lead ECG
- BCVA
- Anterior Segment Evaluation
- Posterior Segment Evaluation
- IOP
- SD-OCT*
- OCT-A (to be conducted at sites with the proper equipment available)*
- FA*
- CFP*
- DRSS score*
- Eligibility Criteria

*SD-OCT, OCT-A (if applicable), FA and CFP will be submitted to the Central Reading Center for eligibility confirmation. A report for SD-OCT will be returned to the site within 48 hours and a separate report with DRSS score will be returned to the site within 72 hours to support eligibility and subsequent randomization

5.1.1.2 Visit 1

The following procedures will be done:

- Medical and Ophthalmic History
- Medication History/Concomitant Medications
- Vital signs and Weight
- Pregnancy Test (pre-dose urine dipstick)
- BCVA
- Anterior Segment Evaluation (conduct pre-dose OU and post-dose SE)
- Posterior Segment Evaluation (conduct pre-dose OU and post-dose SE)
- IOP (conduct pre-dose OU and 30 minutes \pm 15 minutes post-dose SE)
- SD-OCT (conduct pre-dose)
- Eligibility Criteria
- Conduct randomization
- Study Drug Administration
- AE Assessment

5.1.1.3 Visits 2, 10 and 11

- Medical and Ophthalmic History
- Medication History/Concomitant Medications
- Vital Signs and Weight
- BCVA
- Anterior Segment Evaluation
- Posterior Segment Evaluation

- IOP
- SD-OCT for Visits 10 and 11 only
- AE Assessment

5.1.1.4 Visits 3–7

- Medical and Ophthalmic History
- Medication History/Concomitant Medications
- Vital Signs and Weight
- BCVA
- Anterior Segment Evaluation
- Posterior Segment Evaluation
- IOP
- SD-OCT
- OCT-A (to be conducted at sites with the proper equipment available) for Visit 7 only
- FA for Visit 5 and 7 only
- DRSS score at Visit 7 only
- AE Assessment

5.1.1.5 Visit 8

- Medical and Ophthalmic History
- Medication History/Concomitant Medications
- Vital Signs and Weight
- BCVA
- SD-OCT
- AE Assessment

5.1.1.6 Visits 9 and 12

- Medical and Ophthalmic History
- Medication History/Concomitant Medications
- Physical Examination
- Vital Signs and Weight
- Pregnancy Test (urine dipstick)
- Laboratory Tests: Hematology and Chemistry
- 12-lead ECG
- BCVA
- Anterior Segment Evaluation
- Posterior Segment Evaluation
- IOP
- SD-OCT
- OCT-A (to be conducted at sites with the proper equipment available)
- FA
- CFP
- DRSS score
- AE Assessment

5.1.1.7 Unscheduled Visit/Early Termination

- Medical and Ophthalmic History
- Medication History/Concomitant Medications
- Physical Examination
- Vital Signs and Weight
- Laboratory Tests: Hematology and Chemistry
- 12-lead ECG
- BCVA

- Anterior Segment Evaluation
- Posterior Segment Evaluation
- IOP
- SD-OCT
- OCT-A (to be conducted at sites with the proper equipment available)
- FA (only if assessment has not been performed within the preceding 30 days)
- CFP
- DRSS score
- AE Assessment

